Safety and tolerability will be evaluated through assessments of AEs, laboratory analyses (clinical chemistry, hematology, coagulation, urinalysis, creatine kinase-MB [CK-MB], troponin), vital signs, ECGs, ECHOs, cardiac telemetry, and PE examination findings at the time points indicated in the schedule of assessments. PK parameters will be analyzed from the plasma and urine samples collected at the time points indicated in the schedule of assessments.

Dose Escalation Decision Process: Enrollment of subjects in each sequential higher dose level cohort will occur only after completion of a clinical safety review of laboratory, AE, vital sign, ECG (12-lead and telemetry), and PE data for all subjects up through 96 hours post-dose and plasma PK data through 24 hours post-dose, by the Sponsor medical monitor, clinical pharmacologist, and principal investigator (PI) at a dose escalation review meeting. Safety data summaries will be prepared by the PI; PK analyses will be performed by the clinical pharmacologist; and the dose escalation safety review summary and decision will be documented by the PI and clinical

pharmacologist. Based upon safety review and evaluation of the data for each subject, adjustments in the dose escalation scheme for the next cohort may be made, including omission of higher dose cohorts in the event that the safety and PK parameters have been adequately characterized with lower dose cohorts. Where considered appropriate to meet the study objectives, adjustments in the protocol-specified dose escalation for subsequent cohorts are permissible (i.e., an intermediate dose between the previous tolerable dose and the scheduled next higher dose). Dose escalation will be stopped if any one of the stopping criteria are met. The highest dose stated in the protocol will not be exceeded without a protocol amendment.

Criteria for stopping dose escalation for review of the PK and safety data:

- One or more subjects with a treatment-emergent QT interval corrected by Fridericia's formula (QTcF) > 480 ms (Grade 2 per the DMID scale) as determined from bedside ECGs (with repeat ECG). If this occurs, the SMC may consult with an independent cardiologist as needed. If it is deemed acceptable to restart the study following review of the data and discussion with an independent cardiologist, if needed, dosing may resume.

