- One or more subjects experiences an increase in BP that requires acute treatment, or has a confirmed systolic BP > 160 mmHg, or a confirmed diastolic BP > 100 mmHg (Grade 3 per DMID scale). Confirmed BP changes require at least 2 measurements at least 2 hours apart, each measured after at least 5 minutes of supine rest.
- Anaphylactic reaction occurs in 1 subject.
- One or more subjects experience a similar Grade 3 treatment-emergent laboratory abnormality or AE that is suspected to be drug-related as determined by the investigator.
- One subject experiences an SAE.
- A cohort's median AUC from time 0 to 24 hours (AUC₂₄) is $\geq 52,500$ ng.h/mL, equivalent to the NOAEL exposure in cynomolgus monkeys.

Sample Size Justification:

No formal power or sample size calculations were used to determine cohort sizes. Cohort sizes were based upon experience in other SAD Phase 1 studies. A sample size of 6 subjects receiving active drug per cohort should provide adequate characterization of PK and safety assessments within this setting.

Number of subjects (planned):

32 subjects, with 8 subjects enrolled per cohort (6 receiving galidesivir and 2 receiving placebo)

Criteria for inclusion:

1. Able to provide written, informed consent.
2. Males or non-pregnant, non-lactating females age 18–55 years.
3. Body mass index of 19.0 to 32.0 kg/m², inclusive
4. Weight ≥ 50 kg (110 lb.) and ≤ 100 kg (220 lb.)
5. Male and female subjects must agree to the contraception requirements and must meet the inclusion criteria regarding contraception as outlined in the protocol.
6. Has normal vital signs at screening visit at rest, after 10 minutes in a supine position:
 - Oral temperature $< 38^{\circ}\text{C}$; no recent hot or cold beverages

- Resting heart rate is between 60–100 beats per minute (bpm). If a subject is a young healthy volunteer without cardiac disease or symptomatology, heart rate 45–59 bpm will be allowed.
- BP: systolic \geq 90 mmHg and \leq 140 mmHg, diastolic \geq 40 mmHg and \leq 90 mmHg
- Respiratory rate $<$ 20 respirations per minute

7. Suitable veins for cannulation/multiple venipunctures as assessed by the investigator or designee at screening.
8. In the opinion of the investigator, the subject is able and willing to adequately comply with all required study procedures and restrictions for the duration of the study.

Criteria for exclusion:

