In the event that there are any unresolved safety findings that are ongoing at Day 21, the subject will be followed at additional study visits until the findings are resolved or stabilized. If it is determined that the median half-life is longer than anticipated following IV infusion, or if after obtaining PK data through 96 hours, the AUC_{inf} estimate is $> 25\%$ of the AUC from time 0 to the last measurable concentration of drug (AUC_{last}), serial PK sampling may be extended beyond 96 hours in subsequent cohorts, or additional samples may be added in the intervening period between discharge from the CRU and the final follow-up visit (Day 21).

Safety and tolerability will be evaluated through assessments of AEs, laboratory analyses (clinical chemistry, hematology, coagulation, urinalysis, CK-MB, troponin), vital signs, ECGs, ECHOs, cardiac telemetry, and PEs at the time points indicated in the schedule of assessments. PK parameters will be analyzed from the plasma and urine samples collected at the time points indicated in the schedule of assessments ([Table 5](#)).

Enrollment of subjects in each sequential higher dose level cohort will occur only after completion of a clinical safety review of laboratory, AE, vital sign, ECG (12-lead and telemetry), and PE data for all subjects up through 96 hours post-dose and plasma PK data through 24 hours, by the Sponsor medical monitor, clinical pharmacologist, and principal investigator (PI) at a dose escalation review meeting. Rules for halting the escalation to the next dose will be followed as defined in Section [7.6.3.2](#).

Safety and PK data for each cohort will be submitted to the US Food and Drug Administration (FDA) after each cohort is complete. Escalation to the next planned dose may proceed as long as the halting rules are not triggered as defined in Section [7.6.3.2](#).

Figure 1: BCX4430-106 Study Design

Abbreviations: D = day; PK = pharmacokinetic.

Table 5: Schedule of Assessments

Assessment	Screening	In Clinic (CRU) Study Period							Return to CRU for PK Sample	Follow-up or Early Termination Visit
		Day -28 to -2	Day -1 (Admission)	Day 1 Baseline (Pre-dose)	Day 1 (Post dose)	Day 2	Day 3	Day 4	Day 5 (Discharge)	Day 6, Day 8, Day 14 ⁿ
Informed consent	X									
Inclusion/exclusion criteria	X	X								
Medical history	X	X								
Weight/height/BMI	X	X ^a								
Drugs of abuse screen/urine alcohol test/urine cotinine screen	X	X								
HIV/HCV/HBV serology	X									

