7.6.2. Dose Escalation Criteria

As described in Section 11.5.2, at the completion of each cohort, the Dose Escalation Committee (DEC) will meet to review the safety and PK data from the cohort. Dose escalation to the subsequent cohort may proceed without consult with the Safety Monitoring Committee (SMC) as long as none of the following criteria are met:

- One or more subjects with a treatment-emergent QT interval corrected by Fridericia's formula (QTcF) > 480 ms (Grade 2 per the National Institutes of Health [NIH] Division of Microbiology and Infectious Diseases [DMID] scale) as determined from bedside ECGs (with repeat ECG). If this occurs, the SMC may consult with an independent cardiologist as needed. If it is deemed acceptable to restart the study following review of the data and discussion with an independent cardiologist, if needed, dosing may resume.
- One or more subjects experiences an increase in BP that requires acute treatment, or has a confirmed systolic BP > 160 mmHg, or a confirmed diastolic BP > 100 mmHg (Grade 3 per DMID scale). Confirmed BP changes require at least 2 measurements at least 2 hours apart, each measured after at least 5 minutes of supine rest.
- Anaphylactic reaction occurs in 1 subject.
- One or more subjects experience a similar Grade 3 treatment-emergent laboratory abnormality or AE that is suspected to be drug-related as determined by the Investigator.
- One subject experiences an SAE.
- A cohort's median AUC₂₄ is $\geq 52,500$ ng.h/mL, equivalent to the NOAEL exposure in cynomolgus monkeys.

If one of the above safety criteria are met, the SMC will be called to review the safety data from the study. The SMC may make one of two recommendations: to halt the study for further review, or to modify the planned dose escalation to the next dose level. Additionally, the dose escalation may be modified based on review of emerging PK data from any cohort, if needed, in order to refine the escalation to achieve exposure that will not exceed the NOAEL. This review of data may include modeling of planned doses to predict exposure from subsequent cohorts.

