9. TREATMENT OF SUBJECTS

9.1. Treatments Administered

Subjects will be administered a single dose of study drug or placebo per dose cohort as shown below:

Table 7: Dosing per Cohort

Cohort/ Regimen	Dose (mg/kg)	Calculated Dose Range ^a (mg)	Galidesivir Concentration ^b /Placebo	Galidesivir/ Placebo Dose Volume (mL)
1/ A	5	250-500	1.0 mg/mL or placebo	250–500
2/ B	10	500–1000	1.0–2.0 mg/mL or placebo	500
3/ C	15	750–1500	1.5–3.0 mg/mL or placebo	500
4/ D	20	1000–2000	2.0–4.0 mg/mL or placebo	500

^a Based on inclusion criterion No. 4 in Section 8.1, subjects must weigh \geq 50 kg (110 lb.) and \leq 100 kg (220 lb.).

^b Maximum concentration is 4 mg/mL. The lowest concentration of drug used in this study will be 1.0 mg/mL. Rate of infusion and volume infused will be adjusted as required for different concentrations, but the total length of the infusion will remain 60 minutes. Details on calculating infusion volume will be provided in a separate Pharmacy Manual.

Based on PK and safety data emerging from the cohorts, subsequent cohort doses may be modified. Modifications to the planned dose escalation schema may be implemented without modification of the protocol according to the halting/cohort modification rules described in Section 7.6.3. If more than 4 cohorts are required for the SAD, a protocol amendment will be implemented to enable enrollment of further cohorts.

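### Protocol 7.1 cites the study halting rules (7.6.3.2) for dose escalation, but the synopsis, 7.6.2 and 11.5.2 set a different, mostly stricter six-criterion gate

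*Protocol*

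**What the plan says.** Section 7.1 of the protocol names the escalation rule twice. After describing the dose escalation review it says "Rules for halting the escalation to the next dose will be followed as defined in Section" 7.6.3.2. The next paragraph first states that each cohort's data go to the FDA, and then says "Escalation to the next planned dose may proceed as long as the halting rules are not triggered as defined in Section" 7.6.3.2.

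Three other places use a different list of six criteria:

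- The synopsis says "Dose escalation will be stopped if any one of the stopping criteria are met". One of its six criteria is "One subject experiences an SAE".
- Section 7.6.2 says escalation "may proceed without consult with the Safety Monitoring Committee (SMC) as long as none of the following criteria are met", and then gives the six. If one is met, the SMC is called and may recommend a halt or a modified escalation.
- Section 11.5.2 repeats the six, tells the Dose Escalation Committee (DEC) to apply them, and holds planned escalation until the SMC has reviewed the data.

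Section 9.1 has a related pointer. It allows planned doses to change without an amendment "according to the halting/cohort modification rules described in Section 7.6.3". Section 7.6.3 holds only infusion and study halting rules. The modification rules are in 7.6.2, for example "Additionally, the dose escalation may be modified based on review of emerging PK data from any cohort".

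**The concern.** The pointer determines which list gates escalation, and so whether the SMC sees the data. Section 7.6.3.2 serves another purpose: it stops dosing of everyone, in any cohort, and most of its thresholds are higher.

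Under 11.5.3 the SMC meets during the study on three occasions: halting criteria are met, the DEC could not approve escalation, or the criteria after sentinel dosing are met. Suppose the DEC applied 7.1 as written after one non-sentinel subject had a confirmed systolic pressure above 160 mmHg. None of the three would arise, although 11.5.2 requires SMC review. Blood pressure is a relevant example, because 4.2.3 reports rises in conscious monkeys at intramuscular doses above 10 mg/kg.

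Section 7.1 is also at odds with itself. It requires review of 24-hour plasma PK before escalation, yet the list it cites has no PK criterion.

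**Working it through.** The plan states no figure to reproduce here, so the check is mainly a comparison of the two lists.

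| Event | Synopsis, 7.6.2, 11.5.2 | 7.6.3.2 (cited by 7.1; counted across cohorts) |
|---|---|---|
| BP rise needing acute treatment, or confirmed >160 systolic or >100 diastolic | 1 subject | 2 subjects |
| Anaphylaxis | 1 subject | 2 subjects |
| QTcF >480 ms | 1 subject | 2 subjects, or 1 if >500 ms or a rise >60 ms |
| Grade 3 event | 1, suspected drug-related | 2 in one organ class, related or not |
| SAE | any 1 | 1 at least possibly related on galidesivir, or any death |
| Cohort median AUC24 | ≥52,500 ng.h/mL | none |

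The Grade 3 row rests on a reading. Section 7.6.2 says "One or more subjects experience a similar Grade 3 treatment-emergent laboratory abnormality or AE that is suspected to be drug-related", and a single event has nothing to be similar to. I take one subject to be enough.

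**The lists are not nested.** Two Grade 3 events in one organ class that are not suspected to be drug-related can trip only 7.6.3.2. So can a QTcF rise above 60 ms that ends at or below 480 ms, which needs a baseline below 480 − 60 = 420 ms, unless it is judged a drug-related Grade 3 event (Appendix A grades that rise as 3).

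**QTcF, one subject.** Let b be baseline and q the post-dose value. The escalation list trips at q > 480. Section 7.6.3.2 trips at q > 500 or q − b > 60. The band that trips only the escalation list is 480 < q ≤ min(500, b + 60):

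- b = 420: upper end 480, so the band is empty.
- b = 430: upper end 490.
- b ≥ 440: upper end 500, so the whole band.

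Example: q = 485 with b = 450 is a rise of 35 ms and trips only the escalation list. With b = 420 the rise is 65 ms and both trip. Exclusion 3 in 8.2 admits screening QTcF up to 450 ms in men and 460 ms in women. Baseline itself is the Day 1 pre-dose average (11.3.1.4), so these limits show only that such baselines are plausible.

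**AUC24.** The last planned escalation follows the 15 mg/kg cohort. Assuming dose proportionality:

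- From the appended 10 mg/kg report (geometric mean 20,400): 20,400 × 1.5 = 30,600; 30,600 / 52,500 = 58%. That report says AUC may be slightly underestimated.
- From 4.4.3 (about 47,000 at 20 mg/kg): 47,000 × 15/20 = 35,250; 35,250 / 52,500 = 67%.

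Section 4.4.3 projects about 10,000 at 5 mg/kg, so 47,000 / 10,000 = 4.7-fold for a 4-fold dose. A slope of ln 4.7 / ln 4 = 1.116 gives 20,400 × 1.5^1.116 ≈ 32,100 and 47,000 × 0.75^1.116 ≈ 34,100, both inside the same range.

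**How often a one-subject and a two-subject rule disagree.** The documents give no event rates, so these are assumed. In Cohort 1, with 8 subjects and no earlier cohort to accumulate from, the rules differ when exactly one subject has the event: 8p(1 − p)^7. For p = 1%, 2%, 5% and 10% this is 7.5%, 13.9%, 27.9% and 38.3%. This applies to one event type, such as blood pressure.

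**Use in practice.** Three of the dose escalation reports appended to the SAP check vital signs (item 4.0) against 11.5.2. For ECGs (item 5.0), one cites 11.5.2 and two later ones cite 7.6.3.2, which they describe as governing the infusion, although infusion halting is in 7.6.3.1. All three report no clinically significant ECG findings. The 10 mg/kg report says that no PK parameter met halting rules, but 7.6.3.2 has no PK rule.

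**The case against.** The strongest defence is that the operative text is clear. Section 11.5.2 governs the DEC, and 7.6.2 and the synopsis agree with it. A DEC that follows 11.5.2 cannot approve escalation after one confirmed systolic pressure above 160 mmHg, and that is itself an occasion for the SMC to meet. Harm requires the DEC to prefer an overview section to its own instructions. This stands, and it limits the practical risk.

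The second 7.1 sentence also follows the statement about FDA submission. It can be read as saying that escalation need not wait for that submission, and not as a complete gate. That is a fair reading of the second sentence. It does not help the first, which assigns the rules for halting escalation to 7.6.3.2 outright.

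Some gaps are narrow. Anaphylaxis in a galidesivir subject would often also be a possibly related SAE and trip both lists. At projected exposures the AUC24 gap is textual.

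A reader might infer that escalation went ahead on the weaker list, or that the SMC was bypassed. The documents do not support this: the reports show no finding that met one list and not the other, and the blood pressure checks cite 11.5.2. A reader might also infer that every trigger should bar escalation outright. Sections 7.6.2, 7.6.3.2 and 11.5.2 all provide for modification or restart through the SMC.

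**Conclusion.** Section 7.1 is wrong as written. It cites a list that differs from the governing one on all six criteria and is looser on each of them, while reaching further on two points. Applied literally, it would let escalation proceed without SMC review after a first blood pressure event, one QTcF above 480 and up to 500 ms with a rise of at most 60 ms, one unrelated non-fatal SAE, or a cohort median AUC24 at or above 52,500 ng.h/mL. This assumes that no other halting rule has been met, including by earlier cohorts.

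This is an error in a safety decision rule and should be corrected. It is not an open design question, because 11.5.2 makes the intent recoverable. No decision is shown to have turned on it. The differing ECG citations in the appended reports show that both sections were in use as the reference.

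In 9.1 the pointer is incomplete, not simply wrong: 7.6.3 is correct for halting, and 7.6.2 is missing for modification.

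**What to change.** 1. In 7.1, point both sentences to 7.6.2 and 11.5.2.
2. Add one sentence, because the lists are not nested. Suggested wording: Escalation may proceed without SMC review only if none of the criteria in 7.6.2/11.5.2 and none of the cumulative halting rules in 7.6.3.2 is met; if any is met, escalation or dosing waits for SMC review and recommendation as set out in 7.6.2, 7.6.3.2 and 11.5.2.
3. In 9.1, cite 7.6.2 for modification and keep 7.6.3 for halting.

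The cost is three cross-reference edits and one sentence in a protocol amendment, with no new data, procedures or subjects. If the planned cohorts are already dosed, the correction still matters for any cohort added after Cohort 4, which 11.5.3 already makes subject to an amendment.

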7.2. Number of Subjects

It is planned that 32 subjects will be enrolled in the study, with 8 subjects enrolled per cohort. In each cohort, 6 subjects will receive galidesivir and 2 subjects will receive placebo.

Subjects may be replaced as noted in Section [8.5](#).

7.3. Treatment Assignment

Following confirmation of eligibility, subjects will be identified by a unique 5-digit subject identifier (eg, 11001) in which the first digit indicates the study site identifier, the second digit indicates the cohort number and the final 3 digits indicate the subject number. Any replacement subjects will be identified by replacing the third digit “0” with “9”. For example, if Subject 11005 withdraws from the study early, the replacement subject will be numbered 11905 and will receive the same study treatment (ie, active or placebo) as Subject 11005.

Subject numbers will be as follows:

Cohort	Subject Numbers	Replacement Subject Numbers
1	11001 to 11008	11901 to 11908
2	12001 to 12008	12901 to 12908
3	13001 to 13008	13901 to 13908
4	14001 to 14008	14901 to 14908

7.4. Randomization Procedures

The randomization schedules will be generated by an unblinded study statistician. Masking procedures will be as outlined in Sections [7.5](#) and [9.6](#) and will be used to blind study drug.

A computer-generated randomization schedule will be used to randomly assign subjects to galidesivir or placebo. Subjects in each of the Cohorts 1 to 4 will be randomized to galidesivir or placebo in a 3:1 ratio (ie, 6 subjects per cohort will be randomly assigned to receive galidesivir and 2 subjects per cohort will be randomly assigned to receive placebo).

As a safety precaution, on the first day of dosing in all cohorts, 2 sentinel subjects will be initially dosed. The randomization schedule will be generated so that in each cohort 1 sentinel subject is randomly assigned to receive galidesivir and 1 is randomly assigned to receive placebo. Contingent upon satisfactory results as determined by the PI from safety assessments 24 hours post-dosing (e.g., AEs, ECGs, etc. as described in Section 7.6) of the sentinel subjects, the remainder of the cohort may be dosed at least 2 days later (with 5 subjects randomly assigned to receive galidesivir and 1 subject randomly assigned to receive placebo).

7.5. Masking Procedures

This is a double-blind study; treatment assignment within a cohort will be blinded to the PI, clinical staff, study subjects, and the data management team, with the exception of the unblinded

dosing team, if required. As described in Section 9.6, once infusion bags are prepared and labeled, the research pharmacist will mask the IV bag and tubing (ie, with the use of an overlay or masking tape) to blind the color of the solution in the IV bag and in the IV line.

An unblinded dosing team may be utilized in this study if required. Members of the unblinded dosing team will not be involved in any assessments on the study and will only be utilized for dose administration.

The PI or designee(s) will confirm subject eligibility. The unblinded pharmacist at the clinical site will receive a copy of the final randomization schedule from the unblinded statistician for preparation of the study drug. The laboratory performing bioanalytical analysis will also be provided this randomization scheme. The clinical pharmacologist will receive a copy of the randomization scheme to prepare interim PK summaries for dose escalation review meetings. The unblinded clinical pharmacologist will attend all dose escalation review meetings.

Prior to database lock and unblinding, all original randomization materials will be held by quality assurance personnel and blinded staff will not have access to the randomization schedule during this time. Disclosure envelopes are held in a locked cabinet in the clinical unit and will be used in the event of an emergency by the PI.

Access to study drug assignment will be immediately available if the PI deems it necessary to break the study blind in the interest of a subject's medical safety, in case of a medical emergency, to meet regulatory safety reporting obligations, or if warranted during scheduled safety reviews. The PI must contact the medical monitor within 24 hours following disclosure of study drug assignment.

Any request for information on the randomization schedule after initial issue must be made using a randomization disclosure form, except in the case of emergency unblinding, which must be recorded on the emergency unblinding form. Details of any disclosure of the randomization schedule will be documented and filed appropriately.

Breaking the blind for a single subject (or the 2 sentinel subjects) will not affect the blind for the remaining subjects; however, the site must appropriately document the process. Data may be unblinded, if required, for an interim review of PK and safety data.

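### Protocol 7.5 says unblinding one subject leaves the others' blind intact; with fixed 1:1 sentinel and 5:1 remainder groups this is not true in general for a single subject

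*Protocol*

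**What the plan says.** Protocol Section 7.5 (Masking Procedures) says of a code break: "Breaking the blind for a single subject (or the 2 sentinel subjects) will not affect the blind for the remaining subjects". The single-subject part carries no condition. The same sentence asks the site to document the process.

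The allocation is set out in Section 7.4: overall, "6 subjects per cohort will be randomly assigned to receive galidesivir and 2 subjects per cohort will be randomly assigned to receive placebo". Within that, "in each cohort 1 sentinel subject is randomly assigned to receive galidesivir and 1 is randomly assigned to receive placebo", and the remainder is dosed later, "with 5 subjects randomly assigned to receive galidesivir and 1 subject randomly assigned to receive placebo". Section 7.6.1 and SAP Section 6.2 repeat the split. Section 7.3 adds that a replacement subject receives the same treatment as the subject replaced.

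On who is blinded, Section 7.5 says that "treatment assignment within a cohort will be blinded to the PI, clinical staff, study subjects, and the data management team", apart from an unblinded dosing team if one is used. The disclosure envelopes "will be used in the event of an emergency by the PI". Section 7.5 also makes the assignment available at once where a subject's medical safety requires it.

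**The concern.** The group sizes are printed in the protocol that the blinded investigator works from, and the sentinels are recognisable because they are dosed first. Anyone who learns one assignment can therefore infer others, and the sentence in Section 7.5 tells staff that this does not happen.

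Unblinding is foreseeable. Section 7.5 allows it for medical safety, emergencies, regulatory reporting and scheduled safety reviews. One study halting rule in Section 7.6.3.2 concerns a related serious adverse event in a galidesivir-treated subject, so deciding whether it is met needs that subject's assignment.

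What is at stake is the blinding of later judgements on the linked subjects. Safety and tolerability are the primary endpoint (Section 6.1). The investigator or a medically qualified designee assigns relatedness (Section 11.4.2), and one escalation criterion in Section 7.6.2 turns on a Grade 3 event "suspected to be drug-related as determined by the Investigator". SAP Section 17.1.1 tabulates treatment-emergent events by relationship and by severity, with no mark for assessments made once the assignment could be inferred.

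**Working it through.** **Inputs**
- Sentinels: 1 active, 1 placebo (Protocol 7.4, 7.6.1; SAP 6.2).
- Remaining six: 5 active, 1 placebo (same sections).
- Replacement: same treatment as the subject replaced (Protocol 7.3).

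**Step 1. Reproduce the plan's own figure.** Active: 1 + 5 = 6. Placebo: 1 + 1 = 2. This is the stated 6:2, or 3:1. The number of possible schedules per cohort is 2 sentinel orders × 6 positions of the remaining placebo = 12, taken as equally likely. All 12 contain exactly 6 active subjects.

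**Step 2. Before any unblinding.** The chance of being on galidesivir is 1/2 for each sentinel and 5/6 for each of the other six.

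**Step 3. After unblinding.** Keep only the schedules that agree with what has been disclosed, and recount.

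| Unblinded | Other sentinel(s) | Other non-sentinels | Others fully disclosed |
|---|---|---|---|
| One sentinel, active or placebo | known with certainty | stay at 5/6 | 1 |
| Non-sentinel placebo | stay at 1/2 | 5/6 becomes 1 | 5 |
| Non-sentinel active | stay at 1/2 | 5/6 becomes 4/5 | 0 |
| Both sentinels | none left | stay at 5/6 | 0 |

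The 4/5 arises because removing one known active subject leaves 4 active among 5. No information passes between the sentinel pair and the group of six, because each has its own fixed composition.

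**Step 4. How often another subject is fully disclosed.** Of the eight subjects, the two sentinels and the one non-sentinel placebo subject have this effect: (2 + 1)/8 = 3/8. The mean number of others disclosed is (2 × 1 + 1 × 5 + 5 × 0)/8 = 7/8.

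By treatment of the unblinded subject:
- Placebo: both placebo subjects have the effect, so 2/2 = 1.
- Galidesivir: only the active sentinel of the six, so 1/6.

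**Step 5. Sensitivity to who is unblinded.** Let q be the probability that the unblinded subject is on galidesivir, with a random choice within each arm. The chance of full disclosure of another subject is (1 − q) × 1 + q × 1/6 = 1 − 5q/6. At q = 6/8 this is 1 − 30/48 = 3/8. At q = 1 it falls to 1/6.

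**Step 6. Replacements.** These counts are for the eight original subjects. Under Section 7.3, the assignment of a replaced subject is also that of the replacement, so unblinding one discloses the other.

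**The case against.** The case for leaving the text alone has substance. The parenthetical about the two sentinels is correct for the other six, and naming them as a pair suggests authors who knew that their assignments are linked. For five of the eight subjects, a single unblinding fully discloses nobody else and only moves five others from 5/6 to 4/5. If unblinding is prompted mainly by drug-related events, active subjects will be over-represented and 3/8 is too high.

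The route to decisions is narrow. Only one of the six escalation criteria in Section 7.6.2 and one of the six halting rules in Section 7.6.3.2 use relatedness. The other escalation criteria rest on QTcF, blood pressure, anaphylaxis, any serious adverse event and median AUC over 24 hours. Laboratory and vital-sign severity is graded against numeric limits in Appendix A. An unblinded clinical pharmacologist attends every escalation meeting, and no hypothesis is tested.

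All of this stands, and it limits the consequence. It does not make the single-subject statement true. Nor does the existing documentation close the gap: Section 7.5 requires disclosures to be recorded, but because it says the remaining subjects are unaffected, nothing prompts the site to identify those whose assignment has become known.

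A reader might infer that one code break unblinds the rest of the cohort, or that escalation decisions were compromised. The documents do not support either. The two groups do not inform each other, so no single unblinding reveals all eight assignments, and the available text reports no code break. The Cohort 2 dose escalation summary filed with the SAP points to care on this issue: it gives only geometric mean PK results because staggered dosing could have revealed assignments.

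**Conclusion.** The sentence in Section 7.5 claims a property that the allocation in Section 7.4 does not give. It holds when both sentinels are unblinded. It fails completely when one sentinel, the non-sentinel placebo subject or a subject with a replacement is unblinded, and it fails only slightly (5/6 to 4/5) for a non-sentinel active subject.

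The 3/8 figure assumes equally likely schedules, a random choice of the unblinded subject among the eight, and someone who knows the scheme and who the sentinels are. It lies between 1/6 and 3/8 if the choice leans towards active subjects.

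The practical effect is modest. It reaches only judgements on linked subjects that use investigator relatedness or subjective severity and are made after the disclosure. The sentence is worth correcting because it is wrong and the correction is cheap. Sample size, estimates and analysis models are unaffected.

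**What to change.** 1. Replace the sentence in Section 7.5 with wording such as: *Unblinding one sentinel discloses the other. Unblinding the non-sentinel placebo subject discloses the other five non-sentinels as active. Unblinding a non-sentinel active subject slightly changes the odds for the other five. Unblinding a replaced subject discloses the replacement, and the reverse. Unblinding both sentinels does not affect the other six.*
2. On the unblinding form, list the linked subjects whose assignment has become known and treat them as disclosed from that time.
3. In the adverse event listing (SAP Listing 16.2.7.1), flag relatedness and severity assessments of linked subjects made after the disclosure. Linked means the same sentinel pair, the same group of six, or a replacement. A cohort-wide flag would be too broad.
4. For non-urgent disclosures only, record pending relatedness and severity assessments of linked subjects before the code is opened. This must not apply where it would delay the immediate access that Section 7.5 provides.

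The cost is a few lines of protocol text, one field on a form and one listing flag. If dosing has finished, the flag and a statement in the clinical study report on whether any code was broken can still be added.
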